Once potential participants successfully submit their signed consent form, they will receive an onboarding questionnaire to collect more information, including a home address. A Consenting Coordinator will review this information and send the potential participant a text which will include a confirmation of the start date of their baseline period, as well as a link to a short video of what to expect during onboarding to the study. They will be receive an initial study kit including a Fitbit device via mail, and will receive a copy of their electronically signed HIPAA authorization and consent form with a URL to view the informed consent video that they watched previously.

All baseline periods will begin on a Monday. No more than 20 participants will be permitted to begin on the same day. The baseline period will take place over the course of 2 weeks. Potential participants will not receive any melatonin or placebo pills during the baseline period, and they will be asked to refrain from taking any melatonin on their own. Participants will be instructed to continue treating their sleep quality issues as they normally would.

At three randomized times each day during waking hours (identified by the potential participant during their onboarding survey), baseline participants will receive a text message asking them to rate their pain, fatigue, concentration, confidence, mood, and stress levels at that exact moment. Each morning, baseline participants will receive a survey asking a few questions about their sleep quality the previous night using a modified version of the Consensus Sleep Diary, as well as factors that may have contributed to any sleep issues. At the end of the baseline period on Sunday evening, baseline participants will receive a slightly longer survey that includes the Insomnia Severity Index.

During the baseline period, potential participants will be asked to wear their Fitbit all day and night, even while they are sleeping. Participants will be asked to download the Fitbit app to their smart phone. Baseline participants will be instructed to sync their Fitbit device by opening the Fitbit app on their phone at least every two days and to charge their device at least every four days.

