Ten days into the baseline period, a Consenting Coordinator will review individual adherence to Fitbit wear and to survey responses. Adherence to Fitbit wear will be defined as recorded activity of greater than 12 hours a day, and recorded sleeping activity greater than 180 minutes in total. Survey adherence will be defined as submission of a given survey. Baseline participants who do not achieve at least 80% adherence of Fitbit wear and survey submission during the first 10 days of the baseline period will be given until day 14 of the trial to obtain 80% adherence. Those who still do not meet 80% adherence by day 14 will be withdrawn from the study. Those participants who do maintain at least 80% adherence during the baseline period will be randomized to one of two intervention sequences in the pilot study. Participants who are randomized to receive intervention sequences will receive confirmation including their protocol timeline. Participants will also receive a second mailed kit including medication adherence devices containing pills of a 3mg dose melatonin, pills of a 0.5mg dose melatonin, and pills of a placebo. Participants will not know when they are taking 3 mg melatonin, 0.5 mg melatonin or placebo (single blinded). Enrollment will continue until up to 60 participants have been randomized overall, with 30 participants randomized to receive ABCCBA and 30 participants randomized to receive CBAABC.

Each intervention sequence is made up of 6 2-week periods assigning either 3mg dose melatonin, 0.5mg dose melatonin, or placebo. Participants will not be aware of which pill they are taking in assigned intervention weeks. Instead, they will receive a text notification each night asking them to take one pill out of a designated container (A, B, or C) 1 hour before bed. Melatonin or placebo will be tracked remotely through electronic adherence pill bottles that record each event of a pill being removed via a cellular connection to a de-identified dashboard. Throughout each intervention sequence, participants will be asked to refrain from taking additional melatonin on their own.

Melatonin and placebo supplements will be stored at the study team office from delivery until time of dispensation to participants upon their randomization into the intervention period. The supplements will be handled only by study personnel and stored according to labeling. Records of the batch numbers of supplements provided to each participant will be maintained.

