During all intervention weeks (12 weeks total), participants will be asked to continue wearing their Fitbit device each day and night. They will continue to receive 3 randomized text message surveys each day with questions about their pain, fatigue, concentration, confidence, mood, and stress at that current moment, as well as a morning text asking them to report on their sleep quality the previous night, using a modified Consensus Sleep Diary. Morning surveys during the intervention weeks will also include questions about any melatonin or placebo-related side-effects the participant is experiencing. At the end of each intervention period on Sunday evening (every two weeks), participants will receive a slightly longer survey that includes the Insomnia Severity Index. A study phone number and email address will be available as part of each survey to contact the study team

if a participant is concerned about any side effects they are experiencing. Participants will be instructed to contact 911 or go to the nearest emergency room in the event of a medical emergency. In addition, participants will be advised to stop taking their pills if they are concerned about side effects.

Participants may receive additional text messages to those outlined above with important reminders about their protocol (e.g., transition to a new intervention period), or to remind participants to sync their data or charge their devices. We will send a maximum of 5 text message surveys per day during the study, as well as text messages of these reminders and other important study communications.

In the event of an unanticipated circumstance that temporarily prevents a participant from completing study activities (illness, injury, death in the family, etc.), the participant will have the option of pausing their study to resume once their circumstance has been positively resolved.

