- Mean Within-Subject Difference in Self-Reported Side Effects from Baseline, using the average number of days side effects were reported during treatment periods.
- Mean Within-Subject Difference in Device-Recorded Daily Steps from Mean Baseline, using participant Fitbit data
- Mean Within-Subject Difference in Device-Recorded Nightly Sleep from Mean Baseline, using participant Fitbit data

Other exploratory analyses include:

- Google and social media ad metrics
- Social media activity, including but not limited to:
 - Social media conversion rate, defined as total impressions compared to total click-through
 - Cost per social media conversion
- Website activity, including but not limited to:
 - Total number of website visits per traffic source
 - Website bounce rates

Mean user total time on website

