16. WITHDRAWAL OF SUBJECTS

- *Describe anticipated circumstances under which subjects will be withdrawn from the research without their consent*
- *Describe procedures for orderly termination*
- *Describe procedures that will be followed when subjects withdraw from the research, including partial withdrawal from procedures with continued data collection.*

Circumstances under which participants may be withdrawn from the research without their consent include failure to maintain protocol adherence, ,self-reported

adverse side effects to two or more interventions, significant cell phone carrier issues that prevent the participant from receiving study text messages, it is not in the participant's best interest to continue in the pilot, and the pilot study is stopped. We will not withdraw a participant based on non-adherence to wearing their Fitbit, taking their supplement, or completing daily surveys, as this absence of data is useful for feasibility purposes. Because of this, lack of adherence to Fitbit wear, taking the supplements, or completion of daily surveys are not considered protocol deviations.

A potential participant will not be randomized to receive the intervention protocol until he/she has demonstrated at least 80% adherence to continuous Fitbit monitoring (activity recorded > 12 hours/day, and recorded sleep activity) and response to survey questionnaires during the baseline period.

Potential participants will be notified of the possibility of being removed from the study before intervention randomization due to adherence issues in the informed consent. Participants who fail to maintain minimum adherence during baseline will be notified by the research team in the first 10-14 days of baseline participation. These participants will stop receiving notifications and survey prompts and will receive instructions to un-link their Fitbit device. The participant will be able to keep their Fitbit.

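### The side-effect outcome is a change from a baseline that appears not to be measured, counted in days with no denominator and no stated split by condition

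*Combined protocol and SAP*

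**What the plan says.** Section 12 lists 11 outcomes to be analysed at the level of the individual for the participant report: the Insomnia Severity Index (ISI), sleep-diary quality, six momentary ratings, side effects, steps and Fitbit sleep. All 11 are differences from baseline. The side-effect item reads "Mean Within-Subject Difference in Self-Reported Side Effects from Baseline, using the average number of days side effects were reported during treatment periods".

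Section 11 says when side effects are asked: "Morning surveys during the intervention weeks will also include questions about any melatonin or placebo-related side-effects the participant is experiencing". For the baseline fortnight it describes three momentary ratings a day, a morning survey and a closing survey. On the morning survey, "baseline participants will receive a survey asking a few questions about their sleep quality the previous night", together with factors that may have contributed to sleep problems. On the closing survey, "At the end of the baseline period on Sunday evening, baseline participants will receive a slightly longer survey that includes the Insomnia Severity Index". It also states that "Potential participants will not receive any melatonin or placebo pills during the baseline period".

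On missing days, Section 16 says "We will not withdraw a participant based on non-adherence to wearing their Fitbit, taking their supplement, or completing daily surveys". The same section lets a participant who has an adverse event on one option continue without it, skipping the days assigned to it. No passage says how unanswered or skipped days enter the side-effect count.

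**The concern.** A change from baseline needs a baseline value. Here the question seems to be asked only after pills start, and it concerns symptoms attributed to the pill, which cannot arise before any pill is taken. If baseline is set to zero, subtracting it does nothing: the outcome is the treatment count under another name. Any symptom that a participant would have reported under any pill stays in that figure. Only the placebo periods can separate it out.

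A count of days also depends on how many days were observed. The plan allows that number to differ between conditions, and one route to fewer days is removal of an option because of an adverse event. The option that was tolerated worst may then accumulate the fewest side-effect days.

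Section 9 wants the report to help participants choose a preferred intervention, if any, from their data. A side-effect figure that can favour the less tolerated option works against that purpose.

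**Working it through.** The plan gives no figure for this outcome, so there is none to reproduce. Period lengths and rules below come from Sections 11 and 16. All daily rates, answer rates and stopping times are assumptions, because the documents give none.

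**1. Days available.** Baseline is 14 days. Each condition has 2 × 14 = 28 days, and all treatment has 6 × 14 = 84. As the surveys are described, side effects are asked on up to 84 treatment days and on none of the 14 baseline days. The second figure is inferred from the survey descriptions; no sentence says it outright.

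**2. Baseline taken as zero.** Assume 10% of days have a report under both dose and placebo.
- Dose minus baseline: 28 × 0.10 − 0 = 2.8 days.
- Dose minus placebo: 2.8 − 2.8 = 0 days.

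**3. Unanswered mornings.** Expected count = days × share answered × daily rate. Assume a true rate of 20% in both conditions, with 80% and 50% of mornings answered.
- 28 × 0.80 × 0.20 = 4.48 days.
- 28 × 0.50 × 0.20 = 2.80 days.
- 2.80 / 4.48 − 1 = −37.5%, with no true difference.

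With 60% answered on dose and 90% on placebo, and a common rate of 10%, 20% or 30%, the counts differ by −0.84, −1.68 or −2.52 days. The proportion of answered mornings is equal in every case if missingness is unrelated to symptoms.

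**4. An option removed.** Assume 40% of days on the dose, 10% on placebo, and the dose removed after k nights, with skipped days adding nothing.
- For k = 5: 5 × 0.40 = 2.0 days against 28 × 0.10 = 2.8 days. The order is wrong; the proportions are 40% and 10%.
- The order reverses when k × 0.40 < 2.8, that is k < 7. With placebo at 5% or 20% the limits are k < 3.5 and k < 14.
- If the average is taken only over 14-day periods actually started, the limit at 10% is k × 0.40 < 1.4, that is k < 3.5. Then k = 5 gives 2.0 against 1.4 and does not reverse. The text does not say which average is meant.
- At 60% on the dose and k = 5, the counts are 3.0 and 2.8: nearly equal, although the rates differ six-fold.

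**5. Limit of the remedy.** Assume a 20% rate, independent mornings, and stopping at the r-th symptomatic morning within 28 days. The full-exposure count is 28 × 0.20 = 5.6.

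| r | Expected count | Count understated by | Expected proportion |
|---|---|---|---|
| 2 | 1.98 | 65% | 30% |
| 3 | 2.92 | 48% | 26% |
| 5 | 4.45 | 21% | 23% |

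The proportion is inflated when stopping follows symptoms, and the count is deflated. Neither should be shown without the number of answered days.

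**6. The other ten outcomes.** For the eight stated over three treatment periods (ISI, diary, six momentary ratings), (dose − baseline) − (placebo − baseline) = dose − placebo. The baseline cancels exactly. The steps and Fitbit-sleep items do not name the conditions.

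**The case against.** The strongest reply is one of scale. These outcomes feed a report in a feasibility pilot, and Section 23 says the study is not designed to document a specific benefit. Section 11 has the report set the data, side effects included, against the 3 mg, 0.5 mg and placebo periods, so a split by condition is probably intended. A participant whose option was removed after an adverse event already knows that it was. The wrong-direction example uses assumed rates and treats skipped days as adding nothing, which the text does not state. The proposed proportion has a bias of its own. All of this stands and limits the weight of the point. It supplies neither a baseline measurement nor a denominator.

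A reader might also infer more than the documents support:

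- **That the placebo comparison, or precision, is lost because outcomes are referenced to baseline.** For the eight outcomes above it is recoverable by subtraction. A comparison of variances would only compare two displays of the same data.
- **That pauses lower the count.** Section 11 lets a paused participant resume, and defines completion as two full periods of each option. A pause moves the calendar; it does not remove days.
- **That removing an option leaves a fixed time-trend bias.** With a linear drift of b per week and an option removed after its first period, dose minus placebo in CBAABC carries −1b (3 mg) or −3b (0.5 mg) if calendar positions are kept, but 0 or −2b if later periods move up. The documents do not settle which applies.
- **That background headache or sleepiness is documented.** Section 17 lists melatonin side effects and gives no background rates. Misattribution is possible, but it is not shown.

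**Conclusion.** The point holds for the side-effect outcome. As worded it has no apparent measured reference, no denominator and no stated split by condition. It can understate side effects for an option that was stopped or less often answered. The missing baseline is inferred from the survey descriptions, and the survey instruments themselves are not in the documents. The size depends on assumed rates: 37.5% fewer days from unequal answering alone, or a reversed order (2.0 against 2.8 days) after early removal. Both figures require that unobserved days add nothing, and the reversal also requires counting over the whole 28-day condition.

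For the other ten outcomes, stating dose minus placebo is a useful addition and not the repair of a loss. The SUS endpoint does not use any of these data. Under Section 17 adverse outcomes reach the DSMB separately, so this is not a gap in safety oversight. It should be fixed because the fix is cheap and the report is itself under test.

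**What to change.** Define the side-effect outcome as each person's proportion of answered morning surveys that report a side effect, separately for 3 mg, 0.5 mg and placebo. Contrast it within person as 3 mg minus placebo and 0.5 mg minus placebo, and delete the reference to baseline. Beside it, report the number of answered surveys per condition and the number of participants who had an option removed. Note that the proportion is inflated when an option is stopped after symptoms, and is unbiased for missed mornings only if missingness is unrelated to symptoms.

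As an optional addition, show dose minus placebo beside the change from baseline for the other ten outcomes, and name the three conditions in the steps and Fitbit-sleep items.

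The cost is rewording the outcome list and the report template. No new data are needed.

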13. SPECIMEN BANKING

- *If specimens will be banked for future research, describe where the specimens will be stored, how long they will be stored, how they will be accessed and who will have access to the specimens*
- *List the information that will be stored with each specimen, including how specimens are labeled/coded*
- *Describe the procedures to release the specimens, including: the process to request release, approvals required for release, who can obtain the specimens, and the information to be provided with the specimens.*

N/A

14. DATA MANAGEMENT AND CONFIDENTIALITY

- *Describe the data and specimens to be sent out or received. As applicable, describe:*
 - *What information will be included in that data or associated with the specimens?*
 - *Where and how data and specimens will be stored?*
 - *How long the data will be stored?*

- *Who will have access to the data?*
 - *Who is responsible for receipt or transmission of data and specimens?*
- *Describe the steps that will be taken to secure the data during storage, use and transmission.*

Fitbit®

This pilot study uses non-NFC, Fitbit devices to remotely monitor participant activity and sleep. All enrolled participants will be provided with a study account that has been created by the research team with no identifying information to the participant. The email address of the study account contains a unique identifier (e.g., northwellpt25). Data collected will include daily steps, floors climbed, activity intensity, sleep duration, and estimated minutes in sleep stages. A file linking the Fitbit identifier to the study participant will be housed in a Northwell-approved drive to store PHI and be accessible only by members of the study team listed in the IRB application. Coded data from Fitbit will remain stored in a Northwell-approved drive indefinitely.

Medication Adherence Device

We will monitor adherence to supplement/placebo using a Nomi by SMRxT real-time medication adherence system. The Nomi is a medication event monitoring system (MEMS) that tracks pill or capsule usage without active participant input. The system includes a smart bottle that sends event information such as weight changes and bottle movement via a cellular connection to the SMRxT cloud. No patient information or identifying data is stored on the device. Participants will be instructed to return their Nomi devices back to the study team to return to the manufacturer for proper destroying at the end of the study. Compliance data will be available in real-time on a de-identified study dashboard within the Nomi system. No participant information will be stored within the Nomi dashboard system, and only unique study IDs will be used to collect data. The serial number of the device and unique study ID will be linked to subjects in our Northwell secured data management system (REDCap).

Fitabase

This pilot study will use Fitabase to retrieve Fitbit data from participants. Fitabase is a secure, online portal. The Fitbit study account provided to the participants will be linked to an identification number in the Fitabase system (e.g. FLT01). No information that could be used to identify a participant will be stored on Fitabase. Only the research team will have access to data that will be able to connect a research participant to their Fitabase ID. Data collected will include last sync date, battery charge status, daily steps, floors climbed, activity intensity, sleep duration, and estimated minutes in sleep stages. Fitabase will stop tracking participant data at the trial end date selected by the research coordinator. As an added measure, participants will be instructed to remove the Fitbit study account from their device if they plan on keeping the Fitbit.

Eligibility, Consent, and Survey Data

A goal of this pilot study is to help determine Minimal Viable Product (MVP) specifications for the development of a technology platform to support the delivery of Personalized Trials. To achieve this goal, we are partnering with a company (N1Thrive by 4Peacocks) that was formed specifically for the development of technology to support N-of-1 methodology. Data will be collected and stored using N1Thrive by 4Peacocks, a Northwell security-review approved system for collecting and storing research data, including PHI. The study team will have access to all data, including PHI, throughout the study. Coded data using unique generic participant IDs will be shared with 4Peacocks in order to pool results across all projects using the N1Thrive platform. Pooled results will be used to assess gaps in. This analysis will be done by unique identifier. Coded reports will be given back to the study team, who will identify the document before sending to the participant via encrypted messaging.

Interview Data

Qualitative data collected from interviews with research participants will be collected and stored via REDCap, a Northwell-approved system for collecting and storing research data, including PHI.

The study team takes data confidentiality very seriously. Data collected for this research will be maintained on a HIPAA-compliant Northwell-approved SQL database. All members of the research team with access to identifiable and coded data will be trained and included on the IRB submission for approval. Regular meetings will take place with the PI and other members of the study team to ensure protocol adherence and data accuracy. Data collected for this study will be maintained in its original and unaltered source data state in a Northwell-approved SQL database on a Northwell-approved drive to store PHI indefinitely. Data collected under this research may be used for future research in coded format without additional consent as per the consent form participants sign and with appropriate IRB approval as required. Any additional data that must be shared will be done so according to the consent form participants signed. Only research staff listed within this IRB submission will have access to identifiable information. Anonymized data may be stored indefinitely for reference following the conclusion of the study. The participant will be made aware of all data collected in the consenting process.

This research is funded by the NIH, thus a Certificate of Confidentiality has been issued for this research. Certificates of Confidentiality (CoCs) protect the privacy of research subjects by prohibiting disclosure of identifiable, sensitive research information to anyone not connected to the research except when the subject consents or in a few other specific situations.

